6. STUDY DESIGN

6.1 General study design and justification of design

The study design will be randomized, double blinded and placebo controlled. All patients complying our inclusion criteria will be included to the selection procedure. Patients will be informed about the study sequence during preoperative anesthesiological consultation to give their informed consent. Patients` data will be subsequently integrated to the eCRF. Each participant will be linked with a unique identification code which will be used for continuing process. Furthermore, information about sex, date of birth, date of surgery, indication, BMI, ASA classification, medical history and allergies will be recorded. Patients denying informed consent will be excluded from the pool of selected patients.

The intervention to be studied will either be the additional application of systemic lidocaine 1% dosed 1.5 ml/kg LBM to general anesthesia in bariatric surgery or the application of placebo. Patients, randomly assigned to one study group, will be surveyed for 48 hours after completion of surgery, experienced pain, occurrence of PONV, time to first defecation and length of hospitalization will be monitored. The population to be studied will include 140 patients listed for bariatric surgery at the Kantonsspital St. Gallen and fulfilling criteria for inclusion, respectively without criteria for exclusion. Patients, medical practitioner, nurses and investigators will be blinded by utilization of equal appearance and packing of IMPs, which will be fabricated individually for each patient and on request one to two days before surgery by the pharmacy of the Kantonsspital St. Gallen. Each patient will self-evaluate his maximal experienced pain eight-hourly during a sequence of 48 hours after completion of surgery. Study observation ends with study nurses` final visit on second postoperative day 2pm respectively +/- 30 minutes.

6.2 Methods of minimizing bias

Measures taken to minimize or avoid bias include randomization and blinding of participants after they have given their informed consent. Blinding of medical practitioner and medical personel will be conducted by provision of equal looking and packing of IMPs,

which will be fabricated individually for each patient and on request one to two days before surgery by the pharmacy of the Kantonsspital St. Gallen.

6.3 Randomization

Patients selected to participate will be randomized automatically after giving their informed consent using a computerized block randomization process (10 patients per block). Patients will be randomized 1:1 to either “lidocaine group” or “placebo group”.

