7.3 Recruitment and informed consent

Patients' recruitment will take place during preoperative anesthesiological consultation, which regularly takes place two to three weeks prior hospitalization. Patients will be screened for eligibility using a checklist based on inclusion and exclusion criteria and previous medical history. Informed consent will be obtained in all patients prior to inclusion to the study and randomization process. Patients denying inclusion to the study will be documented as having been screened.

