Study intervention: Patients in the “lidocaine group” will receive 1.5 mg/kg lean body mass of lidocaine 1% bolus intravenously after induction of general anesthesia (as soon

as general anesthesia's steady state is accomplished), followed by a continuous infusion of lidocaine 1% with 1.5 mg/kg lean body mass/h during surgery and continued for four hours after completion of surgery or until the discharge from the PACU, whatever comes first. Patients in "placebo group" will receive 0.15 ml/kg lean body mass of saline 0.9% bolus I.V. after induction of general anesthesia (as soon as general anesthesia's steady state is accomplished), followed by continuous infusion of NaCl 0.9% I.V. with 0.15 ml/kg lean body mass/h during surgery and continued for four hours after completion of surgery or until the discharge from the PACU, whatever comes first. Maintenance of general anesthesia and optional application of additional opiates for pain treatment (fentanyl 0.1 - 0.2 mg as an intravenous bolus) during surgery is under discretion of the attending anesthesiologist and is related to the practice of standardized pain management and will be equal in both groups. Similarly, postoperative treatment in the PACU and further on the surgical ward, are under discretion of the clinically responsible physicians, relating to current practice of standardized pain management at the Kantonsspital St. Gallen (Schmerzkarte KSSG).

A detailed graphical version of study sequences is provided in german as follows:

Periode	Ort	Intervention	Details
Anmeldung	Studien- koordination	Screening	Ein- / Ausschlusskriterien evaluieren
		erfüllt	
PAS Termin	PAS	Informed consent	Aufklärung und Einwilligung durch Patienten
		erfüllt	
PAS Termin	PAS	Randomisierung	Zuteilung zur Gruppe Lidocain oder Placebo
OP Datum	OPS 03	Intervention COALAS	- IMP Bolus ab AN steady state - anschliessend Beginn IMP Perfusor - Datenerfassung ACPDMS (Medis, Vitalparameter) - AE, SAE, ADR erfassen
		Transfer	
POD 0	PACU	VAS Monitoring VAS Evaluationsbogen	- IMP Perfusor bis 4 Std. ab "OP-Ende" od. Transfer auf Abteilung - VAS 1.,2.,3.,4. Std. - Datenerfassung ACPDMS (Medis, Vitalparameter) - Prim./Sek. Variablen im CRF erfassen - AE, SAE, ADR erfassen
		Transfer	
POD 0	ABTEILUNG	VAS Monitoring 2pm, 10pm Studiensite 10am, 2pm	- Erinnerung des Pat. durch Pflege- Studienpersonal - Prim./Sek. Variablen im CRF erfassen - AE, SAE, ADR erfassen

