8.3 Packaging, Labelling and Supply

Lidocaini hydrochloridum (Lidocaine Streuli®) will be provided by Streuli Pharma AG, Switzerland (Swissmedic registration number: 300 16).

Saline (Natrii chloridum 0.9%) will be provided by Grosse Apotheke Dr. G. Bichsel AG, Switzerland (Swissmedic registration number: 298 00).

Syringes and ampulles containing the IMPs (Lidocaine 1% or Saline 0.9%) used during the study will be labelled notably. Distinct labels for ampulles and syringes include information about IMPs`origin, charge number, dedicated patient`s ID, fabrication and expiration date (see appendix for a detailed graph of IMP labels). Blinded personel (practitioner, nurses, surgeon, etc.) will not be able to distinguish between the containing IMPs

due to identical appearance and labeling. An additional code to reproduce its origin will also be visible. No special storage conditions are needed for the IMPs. Prepackaging, assembly, blinding procedure and labeling of syringes will be organized by the pharmacy of the Kantonsspital St. Gallen. Personnel related to the peri- and postoperative course (anesthesiology, surgery, PACU, follow-up on surgical ward) will be blinded by the above-mentioned methods. Study specific labeled syringes will be fabricated individually for each patient and on request one to two days before surgery and will be delivered to the OR on the day of surgery and preparation of syringes (connection to syringe pump) will be conducted by anesthesiological employees.

To ensure product safety for human consumption/application, Good Manufacturing Practice will be conducted.

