10.3 Determination of Sample Size

With an expected postoperative VAS/NRS score (any development during first four hours after completion of surgery) of > 3 points in patients undergoing elective bariatric surgery of 65% in the control group, the expected frequency of VAS/NRS score ≤ 3 is 65% in the interventional group. A two group test with a 0.05 two-sided significance level will have 90% power to detect a redistribution of VAS/NRS score ≤ 3 points in favour of interventional group when the sample size in each group is 63. Assuming a 10% dropout rate, 140 subjects will be recruited and randomized. Sample size was calculated according to Jaykaran et al. with a sample size calculation for χ^2 tests using web-based sample size calculator on biomath.info. (55, 56)

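### Randomisation at the consultation two to three weeks before admission, when the allocation is first needed one to two days before surgery, creates avoidable post-randomisation losses

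*Combined protocol and SAP*

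**What the plan says.** Section 6.3 makes randomisation follow consent directly: "Patients selected to participate will be randomized automatically after giving their informed consent using a computerized block randomization process". Section 7.3 places recruitment at the preoperative anaesthesia consultation, "which regularly takes place two to three weeks prior hospitalization". The study-sequence table in section 8.1 (table 2) agrees. Its randomisation row, "Zuteilung zur Gruppe Lidocain oder Placebo", carries the same period label as the consent row (the consultation appointment), and the next row is the day of the operation.

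Study drug comes later. Section 8.3 states: "Study specific labeled syringes will be fabricated individually for each patient and on request one to two days before surgery". The syringes "will be delivered to the OR on the day of surgery". Sections 6.1 and 6.2 give the same preparation window.

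On numbers, section 10.3 says: "Assuming a 10% dropout rate, 140 subjects will be recruited and randomized". Section 7.5 lists participant request and SAE as the grounds for withdrawal and does not mention cancelled surgery or lost eligibility. Section 10.4 describes the two groups as patients receiving lidocaine or saline. Section 10.8 leaves drop-outs out of the statistical analysis. No replacement rule is given.

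**The concern.** The primary outcome is a pain score in the first four hours after surgery, so it exists only for patients who are operated on. Between the consultation and the pharmacy request, elective surgery can be cancelled, a patient can withdraw, and some of the section 7.2 exclusions can newly apply (pregnancy, an opiate prescription, an arrhythmia). Under the present timing each such patient has already taken a randomisation slot. The plan then has a randomised patient without study drug and without an outcome, whom section 10.8 removes.

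Two things are at stake. One is the number of evaluable patients, because a single 10% allowance has to cover losses before, during and after surgery. The other is how close the analysed set stays to the randomised set: each loss in the gap is an exclusion after randomisation that later randomisation would have avoided.

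**Working it through.** **Timing.** Allocation is fixed at the consultation (6.3, 7.3, table 2), regularly two to three weeks before admission. Its first described use is the preparation of syringes one to two days before surgery (6.1, 6.2, 8.3). The exposed interval is therefore most of two to three weeks, and no step in the text between those two points uses the allocation.

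**Reproducing the sample size.** Inputs from 10.2 and 10.3: event rates 65% and 35%, two-sided alpha 0.05, power 90%, 1:1 allocation.

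- Uncorrected: n = [1.960·√(2·0.5·0.5) + 1.282·√(0.65·0.35 + 0.35·0.65)]² / 0.30² = 56.3, so 57 per group.
- Continuity-corrected: n' = (n/4)·[1 + √(1 + 4/(n·0.30))]² = 62.8, so 63 per group. This is the plan's figure.
- Drop-out: 63/0.9 = 70 per group, 140 in total, as stated.

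**Allowance.** 140 − 2·63 = 14 patients, for all causes. At 10% total loss the planned number is met exactly, with nothing in reserve.

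**How much the gap could use.** The documents give no rate, so these are assumptions: losses before study drug of 3%, 5% or 10% are 4.2, 7 or 14 of 140 patients, or 30%, 50% or 100% of the allowance.

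**Power if gap losses come on top of the planned 10%.** Evaluable number per group is 70·(1 − total loss), rounded down, with equal loss in both arms. Power = Φ{[d − 1.960·√(2·0.5·0.5/n)] / √(0.455/n)}, where 0.455 = 2·0.65·0.35. Here d = 0.30 uncorrected, or 0.30 − 1/n with continuity correction.

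| Total loss | n per group | Power, corrected | Power, uncorrected | To randomise for 63 per group |
|---|---|---|---|---|
| 10% | 63 | 90.1% | 93.0% | 140 |
| 15% | 59 | 87.9% | 91.3% | 150 |
| 20% | 56 | 85.9% | 89.9% | 158 |

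**Balance.** If 14 of 140 patients (70 per arm) are lost at random, the standard deviation of the difference in arm size is 2·√(14·0.25·126/139) = 3.6 patients. It is 2.6 for 7 losses and 2.0 for 4. A 59/67 split has 92.9% uncorrected power against 93.0% for 63/63 (90.0% against 90.1% corrected). Imbalance from incomplete blocks is therefore immaterial.

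**The case against.** The timing is not in dispute; the consequences are. The case for leaving the plan alone has five parts.

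- **Postponement.** A reader might infer that every moved operation becomes a randomised drop-out. The documents do not support that: drug is made per patient and on request, so it can be ordered for the new date, and section 7.5 does not remove a patient for a date change. This stands.
- **Bias and balance.** A reader might infer that these losses bias the comparison or undo the 1:1 allocation. No study drug has been given at that stage and patients and carers are blinded (6.4), so the losses should be unrelated to arm. The likely imbalance is a few patients with no practical effect on power. This stands. That the allocation exists for weeks before use is not in itself a harm either, since no route to disclosure is described.
- **Size.** Losses of up to 10% in total are already covered, and 63 is the more conservative figure. Section 10.5 specifies no continuity correction, and for the uncorrected test 57 per group is enough, so 140 − 114 = 26 losses could be borne. This stands, and it keeps the point modest.
- **Eligibility re-check.** A reader might infer that none is planned. The text describes none between randomisation and surgery, but section 9.1 refers to an appendix for the detailed procedures, which is not available here. Its absence cannot be asserted.
- **Alternative remedy.** Defining the analysis set as randomised patients who started study drug would deal with patients who were never operated on, without changing when randomisation happens. That would tidy the analysis, but the slots would still be lost and the exclusions would still follow randomisation.

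**Conclusion.** The point holds as a modest, cheap improvement. Randomising at the consultation has no purpose that the protocol describes, and it turns cancellations, withdrawals and new ineligibility before surgery into randomised patients without an outcome. The harm is avoidable post-randomisation exclusions and a possible loss of power: about 2 percentage points below the planned 90% at 15% total loss and about 4 at 20% (continuity-corrected), and almost none by the uncorrected test.

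These figures assume that losses in the gap add to the planned 10% and fall equally on both arms. The actual rate cannot be judged from the documents, and if all losses together stay within 10% the planned power is kept. It is also assumed that a cancelled patient counts as a drop-out under section 10.8, which does not define the term; with no pain score, such a patient could not enter the primary analysis as planned in any case.

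**What to change.** In sections 6.3 and 7.4 and in table 2, keep consent at the preoperative consultation and move randomisation to the pharmacy request one to two days before surgery. Make it conditional on a documented re-check of the existing section 7 criteria and on a confirmed operation date. Record patients who consent but do not reach that point as 'consented, not randomised', so that they appear in the participant flow without using the 10% allowance.

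The cost is protocol wording and a change in when the randomisation call is made. The block list, syringe preparation and blinding stay as they are. The real burden is that the allocation must be available shortly before each operation. Section 7.4 has the statistician conduct the randomisation while section 6.3 calls it automatic, so the amendment should state how the pharmacy obtains each allocation in time. Losses after the pharmacy request will remain, and the 10% allowance is still needed for them.

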6.4 Blinding procedures

All patients will be blinded to their randomization. Attending physician and other personnel responsible for patients` care (peri- and postoperative) will be blinded. Syringes used for application of interventional drugs will be blinded, labelled as “interventional drug”. Unblinding, in case of SAE or suspected unexpected serious adverse reactions and to guarantee patients safety, will be executed by the Principal Investigator.

6.5 Unblinding procedures

Should it be necessary to unblind a patient for safety or regulatory reasons, the Principal Investigator shall look up the randomization, which will be kept in a separate envelope, containing information about randomization and leads back to specific IMP of each participant of the study.

7. STUDY POPULATION

7.1 Inclusion

Adult patients listed for elective laparoscopic bariatric surgery, age between 18 – 80 will be screened for inclusion.

7.2 Exclusion

The presence of any of the following exclusion criteria will lead to exclusion of the participant:

- Patients without informed consent, contraindication to the class of drugs under study, e.g. known hypersensitivity or allergy to class of drugs or the investigational product, cardiac arrhythmias, liver dysfunction (Child-Pugh classification A, B or C)

- Women who are pregnant or breast feeding
- Patients suffering from central nervous diseases, which affect structure and function of the brain or the spinal cord (including autism, bipolar disorders, catalepsy, depression, encephalitis, epilepsy, locked-in syndromes, meningitis, multiple sclerosis, myelopathy Tourette's syndrom and neurodegenerative disorders like Alzheimer's disease, Huntington's disease and Parkinson's disease)
- Chronic pain with pre-existing enteral or transdermal opiate prescription or any known drug or alcohol abuse.
- Patients with previous enrolment into the current study, enrolment of the investigator, his/her family members, employees and other dependent persons will be excluded from the screening

7.3 Recruitment and informed consent

Patients' recruitment will take place during preoperative anesthesiological consultation, which regularly takes place two to three weeks prior hospitalization. Patients will be screened for eligibility using a checklist based on inclusion and exclusion criteria and previous medical history. Informed consent will be obtained in all patients prior to inclusion to the study and randomization process. Patients denying inclusion to the study will be documented as having been screened.

7.4 Assignment to study groups

Patients given their informed consent will be randomly assigned to either the "lidocaine group" or the "placebo group". Randomization will be conducted by the statistician of the study using a computerized block randomization process (10 patients per block). Patients will be randomized 1:1 to either "lidocaine group" or "placebo group".

7.5 Criteria for withdrawal / discontinuation of participants

The criteria for withdrawal of participants are either the request of participants to be withdrawn from the study or SAE, related to exercise of IMPs or other medication applied during general anesthesia, including signs of cardiac arrhythmia or other evidence of drug incompatibility resulting in hemodynamic instability.

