5.4 Safety outcomes

Vital parameters (blood pressure, pulse rate, oxygen saturation) will be recorded digitally by the electronic acute care patient data management system (ACPDMS) during the peri- and postoperative phase and according to institutional standards. Incidence of any potential adverse events (AE) requiring treatment attributable to lidocaine (e.g. local skin reactions, nausea, vomiting, dizziness, ear ringing, etc.), serious adverse events (SAE) (cardiac arrhythmia with relevant hemodynamic outcome, cardiac arrest) or adverse

events related to opiates (respiratory adverse events, ileus). Other outcomes of interest, precisely PONV will not be accounted for an AE.

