8.5 Dose modifications

If SAE will be recognized, infusion of investigational product will be stopped and arrangements conducted to treat potential adverse effects and ensure patients` safety. The Principal Investigator will be informed about the incident within 24 hours.

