10.8 Handling of missing data and drop-outs

Missing postoperative VAS/NRS scores, required for primary and secondary endpoints, will be handled as interpolation values, calculating an average score between last recorded scores before and after the missing value. Missing data for secondary endpoint PONV or time to first defecation will be handled as no occurrence of PONV (PONV 0) or no defecation yet. In case of drop-out, data collected till patients drop out will be neglected and not taken into account of statistical consideration of the study.

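### Section 7.5 withdraws the participant for a drug-related SAE where 8.5 and 9.3 only stop the infusion, so later outcomes are not secured and, with 10.8, the patient could be left out of the final analysis

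*Combined protocol and SAP*

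**What the plan says.** Section 7.5 covers withdrawal and discontinuation under one heading. It gives two criteria, both for withdrawal of the participant: "request of participants to be withdrawn from the study or SAE, related to exercise of IMPs or other medication applied during general anesthesia". Arrhythmia and drug incompatibility with hemodynamic instability are named as included. There is no category for a patient who stops study drug but stays in the study.

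Section 8.5 gives a different consequence for an SAE: "infusion of investigational product will be stopped and arrangements conducted to treat potential adverse effects". Section 9.3 likewise ends drug administration for an IMP-related SAE. Neither says that the patient leaves the study.

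Section 10.8 states that in case of drop-out, "data collected till patients drop out will be neglected and not taken into account of statistical consideration of the study". The term drop-out is not defined, and safety data are not excepted. Section 10.4 lists the lidocaine group, the placebo group and the whole population (for secondary endpoints), but no intention-to-treat or safety population. Section 10.5 covers primary and secondary endpoints and names no safety analysis.

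The safety outcomes in section 5.4 include "serious adverse events (SAE) (cardiac arrhythmia with relevant hemodynamic outcome, cardiac arrest", together with AEs needing treatment that are attributable to lidocaine, and opiate-related events.

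Chapter 11 requires AEs and SAEs to be collected and entered in the CRF (11.1, 11.9), SAEs to be followed until they resolve or stabilize (11.2), and patients who end the study early with an ongoing SAE or AE to be followed up (11.8).

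**The concern.** Stopping a drug and leaving a trial are different events, and a plan that merges them loses data it could have kept. Two things are at stake.

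The first is efficacy. A patient withdrawn for a drug-related SAE has no secured outcomes after that point. Lidocaine can cause the trigger, so the gaps can depend on treatment, and removing these patients from the analysis breaks the randomized comparison. Section 7.5 also covers SAEs from other drugs given during anesthesia, opioids among them. If lidocaine spares opioids, that route could also differ between the arms, and in the opposite direction.

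The second is safety. The withdrawal trigger in 7.5 overlaps with the serious events counted in 5.4. If withdrawal leads to exclusion under 10.8, the event that should be counted is what removes the patient from the count. There is no data safety monitoring committee (1.3) and no interim analysis (10.6), so the final tabulation is where the arms would be compared.

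**Working it through.** **Step 1. The plan's own figures.** Inputs from section 10.3: "A two group test with a 0.05 two-sided significance level will have 90% power"; pain above 3 in patients "undergoing elective bariatric surgery of 65% in the control group"; and "the expected frequency of VAS/NRS score ≤ 3 is 65% in the interventional group", so 35% above 3 on lidocaine.

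- Uncorrected: n = [1.960·√(2·0.5·0.5) + 1.282·√(0.65·0.35 + 0.35·0.65)]² / 0.30² = 56.3, that is 57 per group.
- Continuity-corrected: (56.3/4)·[1 + √(1 + 4/(56.3·0.30))]² = 62.8, that is 63 per group. This matches "when the sample size in each group is 63".
- With 10% drop-out: 63/0.9 = 70 per group, 140 in total, as stated.

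The point below changes none of these figures.

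**Step 2. What happens to a patient with an IMP-related SAE.**

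- Sections 8.5 and 9.3: the infusion stops, and nothing is said about leaving the study.
- Section 7.5: the event is a criterion for withdrawing the participant.
- Sections 11.2, 11.8 and 11.9: AE and SAE follow-up continues and is documented, also after early termination.
- Sections 9.2 and 9.4: pain, opiate, PONV, defecation and length-of-stay assessments are scheduled, but nothing says that they continue after a withdrawal under 7.5.
- Section 10.8: if this patient is a drop-out, the data collected up to that point are not analysed.

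The trigger is not limited to cardiac arrest. Section 11.6 counts severe IMP reactions as SAEs, and its severe class includes confusion and muscle twitching.

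**Step 3. Size under the literal reading.** The protocol gives no SAE rate. Assume k events among 70 lidocaine patients, with k from 1 to 7; the upper end equals the plan's own 10% drop-out allowance. Incidence with everyone kept is k/70; under 10.8 it is 0/(70−k). For the effect on the primary endpoint, assume further that each such patient has a score above 3 and that all other lidocaine patients are at 35%. The lidocaine rate with everyone kept is then [k + 0.35·(70−k)]/70. If these patients are excluded, it stays at 35.0%. Power is for a two-sided 0.05 test without continuity correction, against 65% in 70 placebo patients.

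| k | SAE incidence, kept | SAE incidence, excluded | Pain rate, kept | Difference from 35.0% | Power, kept | Power, excluded |
|---|---|---|---|---|---|---|
| 1 | 1/70 = 1.4% | 0/69 | 25.15/70 = 35.9% | 0.9 points | 93.9% | 95.1% |
| 3 | 3/70 = 4.3% | 0/67 | 26.45/70 = 37.8% | 2.8 points | 90.5% | 94.8% |
| 7 | 7/70 = 10.0% | 0/63 | 29.05/70 = 41.5% | 6.5 points | 80.2% | 94.1% |

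Exclusion makes lidocaine look better on pain and hides the SAEs. The pain columns are the unfavourable end, because they assume that every such patient has a score above 3.

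**The case against.** A reader might infer that every IMP-related SAE must disappear from the safety statistics, so that the trial would report lidocaine as free of serious reactions by construction. The documents do not support that, for these reasons:

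- The inference needs three steps that the protocol never takes: that withdrawal in 7.5 is the same as drop-out in 10.8, that every such SAE does lead to withdrawal even though 8.5 and 9.3 only stop the infusion, and that 10.8 governs safety reporting. Section 10.8 stands in the statistics chapter beside the rules for missing pain scores, PONV and defecation, while safety has its own chapter.
- Chapter 11 secures the SAE records. They are collected, documented and followed up, also after early termination, and SUSAR and annual safety reports are required. Section 13 also foresees publication of the raw dataset.
- Section 10.5 plans no between-arm safety test that could be forced to zero.
- Section 5.4 is wider than these SAEs. Non-serious AEs are not a withdrawal criterion in 7.5.
- The background in sections 3.2 and 3.5 reports no evidence of higher risk and a comparable incidence of adverse effects, so events may be few. The counts used here are assumptions.
- Some outcome sources, such as electronic anesthesia records and ward charts for opiates, exist as routine documentation. Self-rated pain may be unobtainable after some SAEs.

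All of this stands, and it limits the point to what the text permits. It does not remove it. Collecting an SAE does not ensure that it is counted, and the plan never says in which patients safety is summarized. Routine charts do not replace a rule that the study's scheduled scores and CRF entries continue.

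**Conclusion.** The point holds in a limited form. Section 7.5 does not separate stopping study drug from leaving the study, and it differs from 8.5 and 9.3 on what an SAE leads to. Scheduled efficacy outcomes after such a withdrawal are not secured. Sections 10.4 and 10.8 leave open whether these patients and their SAEs enter the final tabulation; the literal reading excludes them.

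The size depends on that reading and on assumed counts. For 1 to 7 events among 70 lidocaine patients, an incidence of 1.4% to 10% would be tabulated as 0%. If all of these patients also had a score above 3, the lidocaine pain rate would be understated by 0.9 to 6.5 points. With no such events nothing changes. The sample size of 63 per group and 140 in total is unaffected. The wording should be settled before enrolment, because scores that were never taken cannot be recovered.

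**What to change.** 1. In section 7.5, separate two cases and reconcile the text with 8.5 and 9.3. (a) Stopping study drug: the patient stays in the study, and the already scheduled pain, opiate, PONV, defecation, length-of-stay and safety data are collected as far as obtainable. (b) Withdrawal from the study: only when the patient withdraws consent. The clinical trigger for stopping the drug is for the sponsor to decide and is not addressed here.
2. In section 10.4, state that safety outcomes are analysed in all patients who received any IMP, including those stopped early or withdrawn, using data up to withdrawal.
3. In section 10.8, define drop-out, and state that the rule applies neither to safety data nor to patients who only stopped the drug.

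The cost is protocol wording, through the amendment route in sections 2.10 and 10.7. The assessments are already scheduled on the PACU and the ward, so no extra visit or staff is needed. The small downside is that a few patients contribute outcomes after a shortened infusion.
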